	Service Lead, Hull and East Yorkshire Hospitals NHS Trust												
	[name], Patient Representative												
	[name], Patient Representative												
	[name], Patient Representative												
	Independent Study Steering Committee												
	Chair [name], University of Birmingham												
	Member [name], Salford Royal												
	Hospitals NHS Foundation Trust												
	Member [name], University of East Anglia												
	Member [name], Newcastle University												
	PPI Member [name]												

Study Summary

Study Title	PoPSTER: Patient preferences and current Practice for adults with											
	STERoid resistant ulcerative colitis – a mixed methods study											
Short Title	PoPSTER											
Study Design	Mixed methods study design											
Study Participants	Work package 1:											
	Online survey of IBD Healthcare Professionals											
	Work package 2: Interviews with IBD Healthcare Professionals											
	Work package 3: Interviews with patients with ulcerative colitis											
	Work package 4: Discrete Choice Experiment of IBD Healthcare Professionals and patients with UC											
	Work package 5: Multi-stakeholder workshop with IBD Healthcare Professionals and patients with UC											
Planned Size of Sample	Total: n=1150											
	Work package 1: Online survey of approximately 700 IBD Healthcare Professionals											
	Work package 2: 20-25 interviews with IBD Healthcare Professionals											
	Work package 3: 30-35 interviews with patients with UC											
	Work package 4: Discrete Choice Experiment of 180 patients with UC, and up to 200 IBD Healthcare Professionals											
	Work package 5: Multi-stakeholder workshop of up to 20 patients with UC and IBD Healthcare Professionals											
Planned Study Period	November 2018 – October 2020											
Research Aims	The overall aim of this research is to understand how adults with steroid resistant ulcerative colitis are being managed in secondary care, and how current practice compares with patient and clinician preferences.											

Funding

FUNDER	FINANCIAL AND NON FINANCIAL SUPPORT GIVEN
National Institute of Health Research through their Health	Funders of the research programme
Technology Assessment programme (HTA)	
[contact], Email: [contact]	

Role of Study Sponsor and Funder

Neither the funder nor the Sponsor have had any role in study design, data collection and analysis, decision to publish, or preparation of manuscripts.

Role and responsibilities of Study Management Group and Steering Committees

The overall responsibility for the study will be with Sheffield Teaching Hospitals NHS Trust who will act as sponsors for the study. The study will be conducted in accordance with the protocol, GCP and Sheffield CTRU Standard Operating Procedures. The two committees which will govern the conduct of the study are:

1. Study Steering Committee (SSC)

The SSC will be responsible for the overall conduct of the PoPSTER study and consists of an independent chair and four other independent members including a statistician and PPI representative. The committee will meet approximately every 6 months to monitor the study.

2. Study Management Group (SMG)

The role of the SMG is to monitor all aspects of the conduct and progress of the research, ensure that the protocol is adhered to, and take appropriate action to safeguard participants and the quality of the research itself. The SMG will comprise of the Chief Investigator and all co-investigators. The PMG will meet on a regular basis (quarterly) to monitor the day-to-day running of the study.

Protocol Contributors

All co-investigators contributed to the development of the protocol. The protocol was reviewed and the final version approved by [name].

KEY WORDS:	Inflammatory Bowel Disease Ulcerative Colitis
	Preferences Qualitative Research Discrete Choice Experiment

Study Flow Chart

PoPSTER : STUDY DESIGN FLOW DIAGRAM (17/72/02)

1. Rationale

Ulcerative colitis (UC) runs a relapsing/remitting course, with debilitating symptoms, impaired quality of life and severe attacks requiring hospitalisation. For active UC not requiring hospitalisation, oral corticosteroids may induce remission in those refractory to aminosalicylate therapy [1]. Corticosteroids are recommended first line therapy for a severe relapse of UC [2].

Just under 50% of patients do not respond fully [3,4] and relapse on steroid dose reduction, leading to prolonged steroid use and debilitating side-effects. Many subsequent treatment options in the NICE treatment pathway [1] have been the subject of randomised controlled trials (RCTs), comparing individual agents with placebo or steroid comparators; direct 'head to head' comparisons are not available. NICE have recommended that the risks/benefits of methotrexate, ciclosporin, tacrolimus, adalimumab and infliximab should be assessed for the induction of remission in steroid-refractory UC [1]. Subsequently, vedolizumab has also been recommended for use in this population [5] and newer agents, ozanimod and tofacitinib, have demonstrated efficacy in RCTs [6]. Other options, including surgery, have not been the subject of RCTs. These options vary in cost, availability, mode of administration, patient acceptability, and use of healthcare facilities as well as clinician experience in their use, especially for newer agents.

There is no universally adopted definition of steroid resistant UC, which might include clinical, endoscopic and quality of life dimensions. There is also an overlap between those with ongoing symptoms or endoscopic inflammation despite corticosteroids ('steroid resistant') and those who initially respond and then relapse on reducing the steroid dose – 'steroid-dependent'. Both groups have been included in clinical trials of agents used for steroid resistant disease. Many of the pivotal trials – particularly of biologic agents – have included both groups and results of treatment in each group have frequently not been reported separately. In addition, these patients may also be on immunomodulator drugs.

Therefore, although national and international guidance [1,6,7] reflect this range of options, there remains a lack of clarity about:

- a) The definition of steroid resistance (dose and duration of therapy);
- b) The specific applicability of current evidence to a population of patients with UC resistant to corticosteroids; and
- c) The optimum choice of treatment for this group and the importance of factors including patient and clinician preferences, concomitant immunosuppression and prior biological therapy.

2. Background

Ulcerative Colitis is associated with significant disability, psychological morbidity and distress [8–10]. It has significant socioeconomic impact arising from disrupted education and employment [8], with 20 days of household and recreational activities per year typically lost to illness [11]. In 2000, before the widespread use of biological agents, treatment costs for UC colitis were estimated at £3021 per patient per year in the UK [12], and in the EC-inception cohort at €1524 per patient year [13]; substantial costs relate to hospitalization and surgery, which are higher in those under 40 years of age [14] and with drug- refractory cases associated with high costs [15]. This may be reduced by more effective treatment but it is unclear whether newer agents are cost-effective in this population [14].

Oral corticosteroids are associated with significant side effects, which preclude long-term treatment. Long-term use of steroids is regarded as a marker of a poor IBD service [16]. There is insufficient information to inform patients with steroid-resistant UC on the choice of agent, concomitant immunosuppression and the timing of surgery. Although qualitative research highlights the divergent perspectives of medical and nursing staff [17], there are limited published patient perspectives, which are needed to inform the design of future clinical trials. Survey data suggests that patients' ideal therapy would be an effective, oral formulation with fewer tablets, less frequent dosing, and minimal side effects [18].

Evidence to inform the choice between anti-TNF agents, vedolizumab, tacrolimus, methotrexate, in- patient intravenous steroids, tofacitinib, ozanimod, and surgery [1,6,7,19,20] in steroid-resistant UC is limited for a number of reasons. No RCTs compare these treatments head-to-head in terms of clinical or cost-effectiveness and safety nor establish the ideal position of surgery in the treatment pathway.

There is also a lack of a widely adopted definition of steroid resistance. It has been defined as active disease despite prednisolone up to 0.75 mg/kg/day over a period of 4 weeks [6] but this is not reflected in the RCTs from which guidance is drawn. Not all patients included in these RCTs are steroid resistant and frequently results for steroid resistant and steroid dependent disease are not separately reported. For example, a minority of patients included in the pivotal trials of infliximab (IFX) in active ulcerative colitis were taking \geq 20 mg/day prednisolone at trial entry [21], and in trials of adalimumab and vedolizumab, remission rates were not significantly different from placebo in those on corticosteroids [22] or failing corticosteroids alone [23].

The position of surgery also needs evaluation. The optimum timing of surgery is unclear and is likely to differ between patients. In a recently published qualitative study, from our group, we demonstrated that patients wished to undergo surgery when faced with severe restrictions on quality of life [24].

In a health economic assessment [25] from our group, (multi-technology appraisal TA329 [19] of anti-TNF agents) for patients in whom surgery is an option, colectomy was expected to dominate all medical treatment options. For patients in whom colectomy is not an option, infliximab and golimumab were ruled out due to dominance, with the incremental cost-effectiveness ratio (ICER) for adalimumab versus conventional treatment expected to be approximately £50,278 per quality-adjusted life-year (QALY) gained. However, there remains debate about whether surgery should be considered a comparator or an end-point and about when surgery would not be an option. Indeed, in TA342 [5], surgery and tacrolimus were not thought to be suitable comparators for vedolizumab.

These issues illustrate the pressing need for a trial with a clearly defined population of steroid resistant patients to evaluate clinical and cost-effectiveness. In order to develop such a trial, detailed understanding of how best to describe steroid resistance, and of patients and clinicians' views of treatment options and treatment objectives is required. This will allow appropriate identification of equipoise and acceptable invention and comparator arms in a trial.

3. Aims and objectives

The overarching research question for this study is:

How are adults with steroid resistant ulcerative colitis (UC) being managed in secondary care, and how does current practice compare with patient and clinician preferences?

To answer the research question, this mixed methods study has the following objectives:

- 1. Describe current practice in the management of adults with steroid resistant UC and how medical resistance is defined.
- 2. Understand how treatment pathways and definitions of steroid resistance are operationalized in practice.
- 3. Understand patient experiences of different treatment options and approaches to decision making.
- 4. Estimate the relative utility of different treatment options; elicit patient and clinician preferences for these and their willingness to trade between them.
- 5. Make recommendations about future research and treatment options.

This mixed methods study includes survey of clinical practice and qualitative interviews with adults with steroid-resistant UC to understand how they are managed and their treatment preferences. In the survey and interviews with a purposive sample of healthcare professionals, we will explore how they define and treat steroid resistant UC. A discrete choice experiment with patients and clinicians will quantify their preferences and estimate relative utility and willingness to trade between different treatment options. Finally, through a multi-disciplinary stakeholder workshop with patients and healthcare professionals, we will present and discuss the findings from this study to generate recommendations about the future optimum treatment and future research.

4. Study Design and Data Collection, Analysis and Storage

This is a mixed methods study composed of five work packages (WP) using a combination of quantitative and qualitative research methods to help achieve each of the five corresponding objectives: (WP1) cross sectional online survey of healthcare professionals (HCPs), (WP2) qualitative interviews with HCPs, (WP3) qualitative interviews with patients with UC, (WP4) discrete choice experiment and (WP5) multi-stakeholder workshop. The details of the sampling, recruitment, data collection and analysis processes for each of the work packages are now described in sub-sections 4.1-4.5. Details of data storage procedures are detailed in section 4.6. Please refer to appendix 1 for the Gantt chart.

4.1 Work Package 1: Cross-sectional online survey of healthcare professionals

4.1.1 Overview

We will conduct a cross-sectional survey of IBD healthcare professionals in the UK to describe the current management of patients with steroid resistant UC. The survey will also allow us to explore how UK clinicians define steroid resistance, their preferences for different treatments and the factors influencing treatment offers.

4.1.2 Sampling

A survey of approximately 1180 healthcare professionals will be conducted online using the Qualtrics platform. This will include the 950 members of the IBD section of the British Society of Gastroenterology and the 230 members of the Royal College of Nursing IBD Nurses Network. We anticipate a 60% response, based on previous surveys of IBD HCPs [26–28] and therefore our sample size is expected to be 700.

4.1.3 Eligibility and recruitment

Healthcare professionals will be eligible to participate in this survey if they are a member of a medical, nursing or Allied Health Professional staff with a specialist interest or expertise in providing care to patients with IBD (particularly ulcerative colitis) within an NHS Trust in the UK. The membership to the IBD section of the BSG and RCN IBD Nurses Network indicates their interest in this clinical area.

Email invitations will be sent to all current members of these two groups and interested parties will be asked to provide informed consent online before completing the survey. The current section chairs of both groups have confirmed their support for distributing the survey. We will issue the survey with a detailed invitation email explaining the purpose of the study and provide a link to the online questionnaire.

We will also use the survey as an opportunity to identify and recruit healthcare professionals for WP2 by adding a section at the end of the questionnaire to ascertain their willingness to be contacted about an in-depth qualitative interview at a later stage in the project.

4.1.4 Data collection

The data for the survey will be collected online using Qualtrics. Qualtrics is a secure online survey platform, enabling participants to complete the survey via an iPad, tablet, or computer. Where participants request a paper-based questionnaire, this will be returned via freepost to the study team, who will enter the data directly into the online survey. We anticipate that the survey will take approximately 15 minutes to complete.

The aim of the survey is to describe:

- Current management pathways for patients with steroid resistant UC;
- How healthcare professionals define steroid resistance
- Preferences for different treatment options, e.g. vedolizumab, tacrolimus, methotrexate, anti-TNF agents (infliximab, adalimumab, golimumab), surgery
- Factors influencing the offer of treatments, e.g. local protocols, individual clinical preference, supporting research evidence, costs of treatment, perceived patient preference; stage of the disease; side effects

We will also collect demographic information about participants (role, clinical specialty, year of registration etc.) and their department and hospital to help understand how practice varies between regions and hospital types. The collection of this information will also feed in to the purposive sampling strategy for WP2. The survey will include a combination of question types: binary response (yes/no); frequency response (always, sometimes, occasionally, never) or options to be selected from a menu. The content of the survey will be developed by study team, and piloted with local clinicians from the collaborating clinical centres prior to distribution [29].

In order to maximize response rates, we will undertake the following activities:

- The survey will be open for approximately 8 weeks, and up to four reminders will be sent to non-responders encouraging them to complete this.
- Incentive prize draw for participation.
- Advertise the survey on social media via our dedicated study Twitter account and Facebook networks.
- Whilst we anticipate that most potential participants will be able to complete the online questionnaire successfully, they will also be able to request a paper-based version of this.

4.1.5 Data analysis

Quantitative results from the survey will be mostly presented using descriptive statistics. Continuous outcomes will be presented using means and standard deviations or medians and interquartile ranges as appropriate to the data. Categorical data will be presented using frequencies and percentages per category. These results will be presented for all respondents and then further split by variables of interest e.g. centre, job role, geographic location etc. to identify any potential differences in disease management or clinical preference depending on these factors. All results will be extracted using suitable statistical programs such as R or Stata [30,31]. Qualitative results from open-ended questions will be summarised thematically.

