4.2 Work Package 2: Qualitative interviews with HCPs

4.2.1 Overview

We will carry out qualitative interviews with a sample of healthcare professionals with expertise in IBD to understand in more depth how patients with steroid resistance are currently managed. Whilst the survey in WP1 will provide us with a national picture of current service provision, the completion of in-depth interviews with staff will allow us to understand how this is operationalized in clinical practice, and the barriers and facilitators to provision of different treatments.

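### WP1's all-respondent percentages describe responding staff; items about a hospital's own arrangements also need a per-hospital figure before they can support statements about service provision

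*Protocol*

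**What the plan says.** - **Who is asked.** Section 4.1.2 builds the frame from individuals: "950 members of the IBD section of the British Society of Gastroenterology and the 230 members of the Royal College of Nursing IBD Nurses Network". Section 4.1.3 adds: "Email invitations will be sent to all current members of these two groups". Nothing restricts replies to one per hospital or asks a hospital to nominate a respondent.
- **How many.** Section 4.1.2: "We anticipate a 60% response, based on previous surveys of IBD HCPs [26–28] and therefore our sample size is expected to be 700".
- **How results are presented.** Section 4.1.5: "Categorical data will be presented using frequencies and percentages per category. These results will be presented for all respondents". The same sentence goes on to split the results by variables such as centre, job role and location. It states no weighting by hospital and no hospital-level denominator.
- **What is asked.** Section 4.1.1 gives the purpose: "to describe the current management of patients with steroid resistant UC". Section 4.1.4 lists pathways, definitions of steroid resistance, treatment preferences and factors influencing offers. Local protocols appear there as one such factor.
- **What is known about the hospital.** Section 4.1.4 collects respondents' demographic details and "their department and hospital to help understand how practice varies between regions and hospital types".
- **What WP1 is said to deliver.** Section 4.2.1: "the survey in WP1 will provide us with a national picture of current service provision".

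**The concern.** The stated analysis counts people, while one stated use of the result is about services. Where an item has one true answer per hospital, for example whether an established pathway exists, colleagues at that hospital report the same fact several times. A percentage over all replies then counts that hospital once per colleague.

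The plan itself gives reason to think practice may vary with hospital size. Section 4.2.2 uses centre size and teaching status to select interviewees, and its wording places them among factors thought to influence practice. The split by centre displays variation between hospitals but leaves the overall percentage unchanged.

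The WP1 findings structure the WP2 thematic analysis (section 4.2.5). They also enter the convergence coding in section 4.5.2, which compares datasets partly on frequency, and so reach the WP5 workshop. A share of staff reported as a share of services would carry through these steps, and a larger number of respondents would not change it.

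**Working it through.** **1. The plan's own figure.** Frame: 950 + 230 = 1180. Expected replies: 1180 × 0.60 = 708, which agrees with the stated 700 or so (700/1180 = 59.3%). The 700 are individuals. The protocol does not give the number of hospitals, the replies per hospital, or the difference in practice between hospitals.

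**2. The two quantities.** Let hospital *h* have *m_h* respondents, and let *p_h* be 1 if it has the arrangement and 0 if not.

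- Respondent percentage (section 4.1.5) = Σ *m_h p_h* / Σ *m_h*
- Hospital percentage = Σ *p_h* / number of hospitals

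With one hospital of 9 respondents that has a pathway and one of 3 that does not, the first is 9/12 = 75% and the second is 1/2 = 50%.

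**3. General form for two size groups.** Let *f* be the fraction of hospitals that are large, *r* the ratio of respondents per large hospital to respondents per small one, and *pL*, *pS* the practice rates.

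- Large hospitals' share of respondents: *w* = *fr* / (*fr* + 1 − *f*)
- Gap = (*w* − *f*) × (*pL* − *pS*)

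The gap is zero if *r* = 1 or if *pL* = *pS*.

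**4. Illustration (all inputs assumed).** *f* = 0.30, *r* = 3, *pL* = 70%, *pS* = 30%.

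- *w* = 0.90 / (0.90 + 0.70) = 0.5625
- Respondents: 0.5625 × 70 + 0.4375 × 30 = 52.5%
- Hospitals: 0.30 × 70 + 0.70 × 30 = 42.0%
- Gap: 0.2625 × 40 = 10.5 points

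If the practice rates are swapped (*pL* = 30%, *pS* = 70%), respondents give 47.5% and hospitals 58.0%, a gap of −10.5 points. The sign depends wholly on which hospitals have the practice.

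**5. A layout that adds to 700 (also assumed).** There are 200 hospitals: 50 large with 8 respondents each (400) and 150 small with 2 each (300). Large hospitals are 25% of hospitals and 400/700 = 57.1% of respondents. With practice at 70% and 40%, the respondent figure is 57.1%, the hospital figure is 0.25 × 70 + 0.75 × 40 = 47.5%, and the gap is 9.6 points.

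**6. Sensitivity.**

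| Assumed inputs | Gap (points) |
|---|---|
| *f* 0.2–0.4, *r* 2–4, *pL* 70%, *pS* 30–40% | 4.0 to 13.3 |
| Five layouts of 150–250 hospitals summing to 700 replies, practice differing by 20–50 points | 4.3 to 19.0 |
| Same layouts, practice unrelated to size | 0 |

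The first two rows assume that large hospitals have the higher rate. They show how the mechanism behaves and do not estimate its effect in this survey.

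**The case against.** The strongest reply is that the protocol never names the hospital as the target unit. WP1 is a survey of professionals, and the research question in section 3 asks how adults with the condition are managed. If larger teams treat more patients, weighting by respondent may come closer to patients' experience than counting each hospital once. The service-provision phrase is a passing contrast with interview depth in the WP2 overview. The questionnaire is not shown, so the number of items that truly concern a hospital's arrangements is unknown. A pathway item could also mean the sequence an individual clinician follows. The split by centre is planned, section 4.1.5 does not exclude further summaries, and an SAP could add them.

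Much of this stands. A reader might infer that the WP1 percentages are biased towards large centres. The documents do not support that: bias needs a declared target, and neither unequal replies nor a difference in practice by size is given as a figure. A reader might also infer that local protocols should be analysed per hospital, but section 4.1.4 lists them only as an influence on a clinician's offers, which is a respondent-level item.

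One point survives. The percentage that section 4.1.5 sets out cannot by itself support a statement about the share of services, and the split by centre does not turn it into one. The protocol does not claim patient weighting either, and replies follow membership and willingness to respond, not caseload.

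**Conclusion.** The concern holds in a limited form. For any item about a hospital's own arrangements, the all-respondent percentage measures the share of responding staff, whereas section 4.2.1 speaks of service provision. The two agree when practice is unrelated to the number of replies per hospital and differ otherwise. Neither the size nor the direction can be found from the documents; the 10.5-point illustration rests entirely on assumed inputs. For personal definitions, preferences and influences on offers, the respondent is the right unit and the plan is sound.

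This is a low-cost improvement to the reporting, not a demonstrated error. No rule in the protocol turns on a WP1 percentage, so nothing shows that a recommendation would change.

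**What to change.** In section 4.1.5, state the unit for each group of items:

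1. Keep percentages of respondents for definitions of steroid resistance, treatment preferences and factors influencing offers, including local protocols as an influence.
2. For items that ask about the hospital's own arrangements, also report a hospital-level percentage beside the respondent percentage. Weight each respondent by 1 / (number of respondents from that hospital) and give the number of hospitals as the denominator.
3. For those items, report how often respondents from the same hospital disagree. Frequent disagreement would suggest that the item describes individual practice after all.
4. Base statements about service provision on the hospital-level figure.

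The cost is a short addition to the text and one weight variable; hospital is already collected. There are two drawbacks. The effective sample size for these items is smaller than 700 suggests (in the assumed layout above, the denominator is 200 hospitals). Respondents who do not give their hospital drop out of the hospital-level figure, so their number should be reported.
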